5.4 Agent Administration

Starting doses of the agents are as follows:

Enzalutamide is provided as 40 mg soft gelatin capsules in bottles with induction-sealed childresistant caps.

Directions for Administration

Study drug doses should be taken as close as possible to the same time each day. All study patients on enzalutamide will take 4 capsules of study drug once daily unless dose adjustment has been done. Patients randomized to bicalutamide will take 1 tab of 50 mg daily dose. If dosing is missed on one day for any reason, double-dosing should NOT occur the following day. The oral medications can be taken with or without food. Documentation of daily dose will be conducted by patient on a study diary.

Storage and Labeling

Study drug should be stored in a secure location with limited access within the following temperature range: 59°F to 86°F (15°C to 30°C). Bottles will be labeled with the study protocol number, medication or bottle number, contents, directions for use, storage directions. Patients will be instructed to store study drug at room temperature out of the reach of children.

6.0 TOXICITIES TO BE MONITORED AND DOSAGE MODIFICATION:

All toxicities will be graded as per NCI Common Toxicity (CTCAE) version 4.0.

Toxicity evaluation will be done monthly for the first 8 visits starting with day 1 and after that every 3 months until progression. Radiologic evaluation at months 6 and 12 with scans (CT scans and bone scan), and PSA levels every month for the first 8 visits and after that every 3 months. After 12 months radiologic evaluation is required annually while patient is on study.

Dose Reduction/Dose Adjustment

Patients who experience a Grade 3 or greater toxicity that is attributed to study medication, and cannot be ameliorated by the use of adequate medical intervention should have their treatment interrupted until the toxicity improves to a Grade 2 or lower severity. Patients may subsequently be re-started on study drug, including at a reduced dose (80 mg daily of enzalutamide), with the written approval of the PI (or designee). **Any reports of seizure activity for patients randomized to enzalutamide require immediate and permanent discontinuation of this therapy.**

There are no dosage adjustments for hematologic toxicity.

Dosage adjustments for Non-hematologic Toxicity: a.

Diarrhea Toxicity:

The major toxic effect of bicalutamide is moderate diarrhea which is very rarely severe (exclusion of other causes of diarrhea should be considered in severe cases).

The dose modifications for this will be as follows, if diarrhea is attributed to protocol therapy.

1. Grade 2 diarrhea, treat symptomatically with anti-diarrhea drugs.
2. Grade 2 diarrhea unresponsive to symptomatic treatment or Grade 3/4 diarrhea - discontinue bicalutamide/enzalutamide until complete recovery.

ABNORMAL LIVER FUNCTION TESTS (AST, ALT, BILIRUBIN)

Grade 2 or greater toxicity - Stop bicalutamide/enzalutamide; wait until liver function tests (LFTs) including AST/ALT and bilirubin are normal (Grade 1 or less).

Restart treatment when AST/ALT and bilirubin return to normal/baseline. If toxicity (Grade 2 or worse) occurs again, discontinue protocol treatment.

Patients requiring treatment delay greater than 2 months for any reason should be removed from protocol treatment.

Patients may complain of flatulence, bloating and mild "gas pains" which should not result in changes in treatment. Symptomatic treatment should be employed with antacids, simethicone, etc. Unexpected or fatal toxicities (including suspected reactions) assessed by the investigator to be related to study therapy/ies must be reported per serious adverse event reporting guidelines as mentioned.

7.0 STUDY CALENDAR: Visit dates and scans can be within +/- 7 days of planned dates.

Study treatment must start within 7 days of registration. For patients eligible for late induction registration the treatment start date will be the date of initiation of GNRH analogue or antagonist, with or without antiandrogen.

| Test | Pre study ¹ | Day 1 | Mth 1 | Mth 2 | Mth 3 | Mth 4 | Mth 5 | Mth 6 | Mth 7 | Post Mth 7 | F/U ⁴ |
|---------------------------|------------------------|----------------|----------------|-------|-------|-------|-------|-------|-------|--------------|------------------------|
| | | | | | | | | | | Every 3 mths | Every 3 mths off study |
| Hand P | X | X | X | X | x | | | X | X | X | |
| PS | X | X | X | X | X | | | X | X | X | |
| Tox | | | X | X | X | | | X | X | X | |
| VS | X | X | X | X | X | | | X | X | X | |
| EKG | X | | | | | | | | | | |
| CBC | X | X | | | X | | | X | | X | |
| AST | X | X | | | X | | | X | | X | |
| ALT | X | X | | | X | | | X | | X | |
| Alk phos | X | X | | | X | | | X | | X | |
| BUN | X | X | | | X | | | X | | X | |
| lytes | X | X | | | X | | | X | | X | |
| creat | X | X | | | X | | | X | | X | |
| PT/INR ² | X | X | X | X | X | X | X | X | X | X | |
| PSA | X | X | X | X | X | X | X | X | X | X | |
| Testosterone | X | | | | X | | | X | | X | |
| CXR/CT ³ | X | | | | | | | X | | | |
| Bone ³ scan | X | | | | | | | X | | | |
| OS | | | | | | | | | | | X |
| Progression | | X | X | X | X | X | X | X | X | | X |
| Tumor biopsy ⁵ | X ⁵ | | X ⁵ | | | | | | | | |
| CTC ⁵ | | X ⁵ | X ⁵ | | | | | | | | |

1. Pre-study H & P, labs, EKG may be done within 28 days of registration. If Labs, and H and P are done within 72 hours prior to registration=they do not have to be repeated on day 1 of therapy unless clinically indicated.
2. PT, INR to be done only if patient on therapeutic Coumadin and then will need to be repeated at least once every month.
3. Tumor assessment scans must be within 60 days prior to registration for all patients. Bone scans are required for pretreatment and subsequent tumor assessments. CT/MRI of abdomen and pelvis should be done if necessary for tumor assessment. Radiologic assessment with bone scans should be done at 6 and

12 months on study (+/- 1 month) and then annually (+/- 1 month) as long as patient continues on study treatment. For late induction registrations, tumor assessment imaging showing metastatic disease must be available prior to start of androgen deprivation therapy.

4. After completion of therapy patients will be followed every 3 months for disease status and survival.
5. Fresh tissue should be collected pre-therapy. Archival tissue should be submitted within 28 days of registration. Post treatment tumor biopsy (optional) and CTC can be conducted within 28-42 days after registration even for late induction patients. Late induction patients will get CTC at time of study entry and then 28-42 days later.
6. Disease progression is defined as evidence of radiographic progression, a skeletal-related event, or clinical progression. Progression of measurable disease is defined by RECIST 1.1 criteria, or progression of bone metastases or occurrence of new skeletal related event or by PSA per PCWG 2 criteria [Appendix B].

8.0 CRITERIA FOR EVALUATION AND ENDPOINT DEFINITION:

The RECIST 1.1 criteria with unidimensional measurement are to be used for measurable disease response evaluation [14].

Baseline Disease Assessment

Measurable lesions must be accurately measured in at least one dimension

(longest diameter in the plane of measurement is to be recorded) with a minimum size of:

- 10 mm by CT scan (CT scan slice thickness no greater than 5 mm; when CT scans have slice thickness >5 mm, the minimum size should be twice the slice thickness). • 10 mm caliper measurement by clinical exam (lesions which cannot be accurately measured with calipers should be recorded as nonmeasurable).
- 20 mm by chest X-ray.
- Malignant lymph nodes: To be considered pathologically enlarged and measurable, a lymph node must be ≥ 15 mm in short axis when assessed by CT scan (CT scan slice thickness is recommended to be no greater than 5 mm). At baseline and in follow-up, only the short axis will be measured and followed.
- Lytic bone lesions or mixed lytic-blastic lesions with identifiable soft tissue components that can be evaluated by cross-sectional imaging techniques such as CT or MRI can be considered measurable if the soft tissue component meets the definition of measurability described above. • ‘Cystic lesions’ thought to represent cystic metastases can be considered measurable if they meet the definition of measurability described above.

However, if non-cystic lesions are present in the same patient, these are preferred for selection as target lesions.

Non-measurable lesions

Non-measurable lesions are all other lesions, including small lesions (longest diameter <10 mm or

Pathological lymph nodes with 10 to <15 mm short axis), as well as truly non-measurable lesions.

- Blastic bone lesions are non-measurable.

- Lesions with prior local treatment, such as those situated in a previously irradiated area or in an area subjected to other loco-regional therapy, are usually not considered measurable unless there has been demonstrated progression in the lesion.

Target Lesions

- All measurable lesions up to a maximum of two lesions per organ and five lesions in total, representative of all involved organs, should be identified as target lesions and recorded and measured at baseline.
- Target lesions should be selected on the basis of their size (lesions with the longest diameter) and be representative of all involved organs, as well as their suitability for reproducible repeated measurements.
- All measurements should be recorded in metric notation using calipers if clinically assessed. A sum of the diameters (longest for non-nodal lesions, short axis for nodal lesions) for all target lesions

Non-target Lesions

All lesions (or sites of disease) not identified as target lesions, including pathological lymph nodes and all non-measurable lesions, should be identified as non-target lesions and be recorded at baseline. Measurements of these lesions are not required and they should be followed as 'present', 'absent' or in rare cases, 'unequivocal progression'.

Evaluation of target lesions

Complete Response (CR): Disappearance of all target lesions. Any pathological lymph nodes (whether target or non-target) must have reduction in short axis to <10 mm.

Partial Response (PR): At least a 30% decrease in the sum of diameters of target lesions, taking as reference the baseline sum of diameters.

Progressive Disease (PD): At least a 20% increase in the sum of diameters of target lesions, taking as reference the smallest sum on study (this may include the baseline sum). The sum must also demonstrate an absolute increase of at least 5 mm.

Stable Disease (SD): Neither sufficient shrinkage to qualify for PR nor sufficient increase to qualify for PD.

Confirmation

In non-randomized trials where response is the primary endpoint, confirmation of PR and CR is required to ensure responses identified are not the result of measurement error. This will also permit appropriate interpretation of results in the context of historical data where response has traditionally required confirmation in such trials. However, in all other circumstances, (i.e., in randomized phase II or III trials or studies where stable disease or progression are the primary endpoints), confirmation of response is not required since it will not add value to the interpretation of trial results. However, elimination of the requirement for response confirmation may increase the importance of central review to protect against bias, in particular in studies which are not blinded. In the case of SD, measurements must have met the

SD criteria at least once after study entry at a minimum interval (in general not less than 6–8 weeks) that is defined in the study protocol.

8.1 Primary Endpoint:

The proportion of patients on either arm achieving a PSA nadir of 4 or less (< 4 ng/ml) at month 7 of protocol therapy.

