3.2 Bicalutamide (Casodex®) (NSC-722665)

For bicalutamide, goserelin acetate, and leuprolide acetate, commercially

Available preparations are used as per the FDA approved dose, route and schedule. Information about commercial drugs is publicly available in the Physician's Desk Reference (PDR), prescribing information and other resources.

Chemistry: Bicalutamide is a racemic mixture containing two enantiomers, (2RS)-4'-Cyano-3(4-fluorophenylsulphonyl)-2-hydroxy-2-methyl-3'-trifluoromethyl propionanilide. Bicalutamide is an active non-steroidal antiandrogen and its antiandrogen activity resides exclusively in the (-) or (R) enantiomer. Unlike flutamide, it is peripherally selective and does not cause a rise in serum LH or Testosterone in male rats and dogs. This peripheral selectivity may be because it penetrates poorly the CNS and Hypothalamus (the site of negative feedback of androgens). In humans, rises in LH, Testosterone and Estradiol concentrations were seen. These rises were not dose related. In 90%, testosterone levels remained within normal limits. There was no significant rise in mean serum FSH.

Bicalutamide has been given to over 3,500 men in 35 different clinical studies worldwide, in doses up to 600 mg daily.

Adverse Effects:

When bicalutamide is given in combination with an LHRH analog, the pharmacologic adverse event profile is dominated by the LHRH analog and includes hot flashes (53%), gynecomastia (9%) and breast pain (6%). Other adverse events reported regardless of causality included diarrhea (12%), constipation (22%), nausea (15%) and abdominal pain (11%). Other adverse events were reported, such as fatigue (22%), pain (35%), back pain (25%), pelvic pain (21%), infection (18%), peripheral edema (13%), dyspnea (13%), nocturia (12%), hematuria (12%), anemia (11%), dizziness (10%). Bicalutamide has been associated with changes in liver function, although these are infrequent (7%) and rarely occur with jaundice.

Many of these changes improved or resolved despite continuation of bicalutamide therapy. There have been no reports of fatal hepatotoxicity associated with bicalutamide therapy.

Pharmacology

Pharmacokinetics:

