10. Willingness to swallow pills and no medical condition that would interfere with this.
11. Male patient and his female partner who is of childbearing potential must use 2 acceptable methods of birth control (one of which must include a condom as a barrier method of contraception) starting at screening and continuing throughout the study period and for 3 months after final study drug administration. Patients are also required to use a condom if having sex with a pregnant woman.
12. Patient should agree to a tumor tissue biopsy prior to protocol enrollment. Post therapy biopsy is optional.
13. Patients who are being treated with a GNRH antagonist should be willing to switch to a LHRH analogue after registration.
14. Patients must have one of the following a) Low volume disease (defined as no visceral metastases and < 4 bone metastases) or b) are not candidates for docetaxel based chemotherapy or 3) refused docetaxel chemotherapy

4.2 Patients must NOT meet any of the following exclusion criteria:

1. History of seizure or any condition that may predispose to seizure (e.g., prior cortical stroke, significant brain trauma) at any time in the past. Also, history of loss of consciousness or transient ischemic attack within 12 months of Day 1 visit;
2. Known or suspected brain metastasis or active leptomeningeal disease;
3. Severe concurrent disease, infection, or co-morbidity that, in the judgment of the Investigator, would make the patient inappropriate for enrollment;
4. Absolute neutrophil count < 1,000/ μ L, or platelet count < 50,000/ μ L, or hemoglobin < 8 /dL) at the Screening visit.
5. Total bilirubin, alanine aminotransferase (ALT) or aspartate aminotransferase (AST) > 2.5 times the upper limit of normal
6. Creatinine > 177 μ mol/L (2 mg/dL)
7. Clinically significant cardiovascular disease including:
 - Myocardial infarction within 6 months;
 - Uncontrolled angina within 3 months;
 - Congestive heart failure New York Heart Association (NYHA) class 3 or 4, or patients with history of congestive heart failure NYHA class 3 or 4 in the past, unless screening echocardiogram or multi-gated acquisition scan performed within 3 months results in a left ventricular ejection fraction that is \geq 45%;

---History of clinically significant ventricular arrhythmias (e.g., ventricular tachycardia, ventricular fibrillation, torsades de pointes);

---History of Mobitz II second degree or third degree heart block without a permanent pacemaker in place;

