Orchiectomy/LHRH analogue Leuprolide or Goserelin or any other FDA approved preparation, approved by PI on notification, except GNRH antagonist such as Degarelix) If patients are late induction and have started on degarelix (Firmagon;Ferring pharmaceuticals) or any GNRH antagonist they will need to be switched to a GNRH analogue.

and

Enzalutamide 160 mg (4Caps of 40 mg each) orally daily (experimental arm)

OR

ARM B

Orchiectomy/LHRH analogue Leuprolide or Goserelin or any other FDA approved preparation, approved by PI on notification, except GNRH antagonist such as Degarelix)

If patients are late induction and have started on degarelix(Firmagon;Ferring pharmaceuticals) or any other GNRH antagonist they will need to be switched to a LHRH/GNRH analogue.

and

Bicalutamide 50 mg orally daily (standard arm).

Stratification by ethnic origin (African American or other) and bone pain (Yes/No).

Patients should continue on study therapy after month 7 unless any of the criteria in section 9.0 for withdrawal are met

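### The liver stopping rule depends on bilirubin, but the study calendar schedules AST and ALT without it (minor safety-consistency correction)

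*Combined protocol and SAP*

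**What the plan says.** The liver rule in Section 6.0 is headed "ABNORMAL LIVER FUNCTION TESTS (AST, ALT, BILIRUBIN", and it applies to bicalutamide and enzalutamide alike. Its first step is "Grade 2 or greater toxicity - Stop bicalutamide/enzalutamide; wait until liver function tests (LFTs) including AST/ALT and bilirubin are normal", where normal is taken as Grade 1 or less. Restart requires AST/ALT and bilirubin to be back at normal or baseline. The last step is "If toxicity (Grade 2 or worse) occurs again, discontinue protocol treatment".

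The Section 7.0 calendar lists laboratory tests one by one. AST and ALT are marked pre-study, on day 1, at months 3 and 6, and every 3 months after month 7. Alkaline phosphatase, BUN, electrolytes and creatinine follow the same pattern. Footnote 1 lets sites skip day 1 labs that were done within 72 hours before registration: "they do not have to be repeated on day 1 of therapy unless clinically indicated".

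Bilirubin appears in one other place, exclusion 5 in Section 4.2: "Total bilirubin, alanine aminotransferase (ALT) or aspartate aminotransferase (AST) > 2.5 times the upper limit of normal". Clinical toxicity review is set in Section 6.0: "Toxicity evaluation will be done monthly for the first 8 visits starting with day 1 and after that every 3 months until progression". Exposure is open-ended under Section 5.3: "Patients should continue on study therapy after month 7 unless any of the criteria in section 9.0 for withdrawal are met".

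**The concern.** A dose-modification rule needs a measurement behind it. Here one of the three named triggers is not on the schedule of tests. A site that performs exactly what the calendar lists has no bilirubin value to grade in a patient who has no symptoms and whose AST and ALT are normal. That patient would stay on a drug that Section 6.0 says to stop. The same applies after a hold: once treatment restarts, a recurrent isolated rise should end protocol treatment, yet nothing scheduled would reveal it.

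The liver rule is deliberately stricter than the general one. For other toxicities, Section 6.0 interrupts treatment only at Grade 3 or above, and only when the event is attributed to study drug and cannot be managed medically. The liver rule acts at Grade 2.

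There is also a small effect on the safety data. Section 12.2 counts a laboratory abnormality as an adverse event if it requires interruption of study drug, and secondary objective 4 compares toxicity rates by arm. Without a scheduled test, finding such events depends on local habit across six institutions.

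**Working it through.** The plan states no figure on this point, so the check compares the rule with the schedule. The added tests are then counted.

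**1. Tests named by the rule against tests scheduled**

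| Test | Named in the Section 6.0 liver rule | Scheduled in Section 7.0 |
|---|---|---|
| AST | yes | pre-study, day 1, months 3 and 6, then every 3 months after month 7 |
| ALT | yes | same visits |
| Bilirubin | yes | none |
| Alkaline phosphatase | no | same visits as AST |

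The remaining laboratory rows are CBC, BUN, electrolytes, creatinine, PT/INR, PSA and testosterone. No row is a liver or metabolic panel, and none of the six footnotes adds bilirubin. The chemistry rows run on without a visible break, so a row lost in text extraction is unlikely.

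**2. Which parts of the rule still work**

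- A rise in AST or ALT is detectable at the scheduled draws.
- During a hold, Section 6.0 itself calls for bilirubin before restart. Something else must first have triggered the hold.
- Jaundice that can be seen or felt may be found at toxicity visits. The toxicity text names no laboratory test, so a silent rise would not be found this way. The calendar's toxicity row is also blank at months 4 and 5, although Section 6.0 says monthly.
- At screening, exclusion 5 implies a bilirubin test, although the pre-study column does not list one.

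What remains uncovered is an asymptomatic, isolated bilirubin rise on treatment, or its recurrence after restart.

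**3. Size of the gap per patient**

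Scheduled on-treatment draws of AST and ALT: months 3 and 6, then 12 / 3 = 4 a year. Scheduled bilirubin tests over the same period: 0.

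**4. Assays added by closing it**

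Input: 92 patients (Section 11.5.1). The pre-study test is left out because exclusion 5 already implies it.

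- Through month 6 (day 1, months 3 and 6): 92 × 3 = 276 at most. Of these, 92 × 2 = 184 fall at months 3 and 6. The total is lower where day 1 labs are waived.
- After month 7: 4 per patient-year. If all 92 stayed on treatment, 92 × 4 = 368 a year. If half did, 46 × 4 = 184 a year. The documents give no retention figure, so both fractions are assumptions.

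**5. Longest interval left after the fix**

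Day 1 to month 3 and month 3 to month 6 are 3 months each. If the first visit after month 7 falls at month 10, the interval from month 6 is 10 − 6 = 4 months.

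**The case against.** The strongest reply is that this is a clerical omission with little consequence. The calendar does not claim to be exhaustive: exclusion 5 cannot be checked without a bilirubin test that the pre-study column also omits, so sites must already order bilirubin outside the calendar at least once. Section 6.0 treats bilirubin as one of the liver function tests, and many sites may receive it in a routine chemistry panel. Alkaline phosphatase is drawn at every AST/ALT visit and could prompt a bilirubin test.

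The expected harm also looks small. Section 3.2 puts liver-function changes on bicalutamide at 7%, rarely with jaundice and with no fatal hepatotoxicity reported; "Many of these changes improved or resolved despite continuation of bicalutamide therapy". Section 2.0 gives liver abnormalities in 1% on enzalutamide against 2% on placebo. If those rates carried over to 46 patients per arm (an assumption), liver abnormalities of all kinds would number about 0.07 × 46 + 0.01 × 46 = 3.22 + 0.46 ≈ 3.7 patients. Isolated Grade 2 or greater bilirubin rises would be a part of that.

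Much of this stands, and it is why the point is minor. It does not remove the mismatch. No text schedules the test or requires a panel, and alkaline phosphatase is only partial cover because bone metastases may raise it too. Whether a given site would measure bilirubin anyway cannot be known from the documents, and a stopping rule should not rest on that.

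**Conclusion.** The concern holds. Section 6.0 makes bilirubin a trigger for stopping, restarting and permanently discontinuing treatment, and Section 7.0 schedules no bilirubin test on treatment. The gap is confined to asymptomatic rises with normal AST and ALT, and to their recurrence after restart. It lasts as long as the patient stays on study drug.

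Few patients are likely to be affected. No expected count of missed cases is given, because the documents report no rate for isolated Grade 2 or greater bilirubin rises. The primary endpoint, the primary analysis and the sample size are unaffected. The conclusion about the missing row is firm; whether any patient would in practice go untested depends on local laboratory practice, on which the documents are silent.

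**What to change.** Add a total bilirubin row to the Section 7.0 calendar at every AST/ALT time point: pre-study, day 1, months 3 and 6, then every 3 months after month 7, with the same day 1 waiver as the other labs. The pre-study entry would also schedule the test that exclusion 5 needs and record the baseline to which the restart rule refers.

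The cost is one extra assay on each existing chemistry draw, within the ceilings worked out above, and no extra visit or venepuncture. The change does not give continuous cover: a rise that comes and goes between draws could still be missed, for up to about 3 months, or about 4 if the post-month-7 visits are counted from month 7.
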